The Emotional Adaptation to Relationship Dissolution Assessment (EARDA) is a 10-item scale developed in the UK and validated in samples of separated parents. The EARDA has excellent convergent, discriminant, concurrent criterion-related, and incremental validity, correlates with co-parenting communication, mediates between separation characteristics and conflict,

and in a small sample, has been found to align with the professional opinion of mediators regarding parents' ability to communicate without arguing (Millings et al., 2020). Because the EARDA's focus is adaptation to dissolution of the relationship, it will only be used where parents are separated. As such, analyses using the EARDA will be regarded as exploratory, as it is not possible to estimate prior to the pilot phase how many separated vs intact families will be referred to the project. The SHU funded PhD studentship opportunity (worth £84K) provides the flexibility in staffing resource to undertake this work, and this component of the project represents added value beyond the evaluation itself.

Socio-demographic information

In addition to the validated outcome measures listed above, parents will also be asked to report socio-demographic information at baseline, e.g., age, sex, gender, ethnicity, LGBTQ+ status, education level, marital status, employment status, and postcode (so that an index of deprivation for participants' neighbourhoods may be found). This will enable examination of the extent to which economic disadvantage affects IPC. We will also ask participants to report their children's ethnicity and sex, whether their children have any special educational needs or disabilities, and whether they are looked-after children/previously looked-after children. We will collect children's dates of birth and home addresses to allow children to be matched to the records held in the National Pupil Database by the Department for Education at the end of the project.

MBT-PP administrative data

For participants allocated to the MBT-PP condition, we will also collect data from TR about the date of first contact with each family, how many therapy sessions were attended per family, how many therapy sessions were delivered and recorded per therapist, and how many hours of supervision therapists received.

Compliance

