The primary analyses will include all CYP in the ITT sample with complete baseline/outcome data regardless of whether their family is classed as being 'compliant' (i.e. by completing 6+ sessions of MBT-PP). To estimate the impact of the Tavistock programme for CYP from families classed as 'compliant', we will undertake two analyses for the SDQ primary outcome; a per-protocol (or on-treatment) and Compliers Average Causal Effect (CACE) analysis. The on treatment analysis would restrict the Tavistock intervention group to only include CYP from families who received 6+ sessions of MBT-PP and compare SDQ outcomes with the complete CYP sample randomised to receive TAU. To accompany the on-treatment analysis, a descriptive comparison of the compliant, non-compliant CYP / family samples will be presented to examine whether it is reasonable to assume that compliant and non-compliant families are 'similar' (the validity of on-treatment analyses is based on this). If compliant and non-compliant families are systematically different, this provides clear evidence that randomness within the on-treatment analyses has been undermined. The CACE analysis would attempt to address the bias within the on-treatment analysis by adopting an instrumental variable (IV) approach using a two stage Least Squares (2SLS) analysis (Sussman & Hayward. 2010; Tilbrook et al. 2014). The first stage would model the binary compliance measure using the baseline SDQ along with additional variables at the CYP and family levels. This model will be used to generate the predicted compliance for the Tavistock programme. The second stage model will then use the predicted compliance variable in place of the group identifier to generate the CACE estimate for the Tavistock programme. In the event of the on-treatment and CACE estimates being closely aligned, we would favour the reporting of the on-treatment estimate for communicability reasons because it is less abstract / technical compared to CACE. However, if notable differences between the on-treatment and CACE estimates are observed, we would favour the CACE estimate because of this attempts to address the potential bias within on-treatment (i.e. families who comply being different from families that do not comply). STATA IVRegress will be used for this IV approach for estimating CACE.

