This trial is running in 3 local authorities, Bristol, Dorset, and Bournemouth, Christchurch, and Poole (BCP). In each local authority, this evaluation funds a 'Gateway Lead' post. Postholders are staff with experience of working with CYP and families and have backgrounds in primary teaching and family support.

Gateway Leads have created referral pathways into the project and promoted awareness of the project in schools and other relevant local authority staff. When referred, families are screened for eligibility against exclusion and inclusion criteria and taken through the consent

process. Once consent is obtained, families complete baseline assessments, and are subsequently randomly allocated to receive either MBT-PP or TAU. Allocation is conducted by the evaluator according to a minimisation protocol to ensure a balanced sample. Families then undergo their allocated treatment. Once treatment has completed, families complete post-intervention assessments. Follow up assessments are completed 3 months later.

The primary outcome variable for this trial is the ‘Total Difficulties’ (TD) subscale of the Strengths and Difficulties Questionnaire (SDQ; Goodman, 1997) obtained from the mothers’ post-intervention assessment, reporting on the CYP. As such, analyses will focus on comparing mothers’ post-intervention TD scores between MBT-PP and TAU. Secondary outcome variables are fathers’ post-intervention TD score; and child psychological well-being (as measured by the Stirling Children’s Well-being Scale, Liddle & Carter, 2015).

The trial is also assessing proposed mechanisms of action, by assessing: parent report IPC (as measured by the O’Leary-Porter Scale, OPS, Porter & O’Leary, 1980, adapted as described in the protocol); child perception of IPC (as measured by the Perceptions of Interparental Conflict-Intensity/Frequency Scale, PIC-I/F, Kline, Wood & Moore, 2003); parent anger (as measured by the Dimensions of Anger Reactions-Revised, DAR-R, Nederlof et al., 2009); parent mentalising capacity (as measured by the Parental Reflective Function Questionnaire, PRFQ, Luyten et al., 2009); parenting style (as measured by the Parenting Scale Short Form, PS-8, Kliem et al., 2019); and, for separated parents only, parent emotional adaptation to separation (as measured by the Emotional Adaptation to Relationship Dissolution Assessment, EARDA, Millings et al., 2020).

Table 1. Trial design overview

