	Level 3 (cluster)	0.01 to 0.15	0.27
Alpha		0.05	0.05
Power		0.80	0.80
One-sided or two-sided?		Two	Two
Average cluster size		2 CYP per family	1.4 CYP per family
Number of clusters	Intervention	175	125
	Control	175	125
	Total	350	250
Number of participants (CYP)	Intervention	350	175
	Control	350	175
	Total	700	350

The power analyses published in the protocol included key parameters for which no empirical estimates could be obtained. Specifically, these were covariate explanatory power (from the baseline mothers SDQ measure) at CYP and family levels and the family level ICC for the mothers SDQ measure at outcome. The protocol used relatively wide ranges of values for CYP and family level explanatory power (between 0.25 and 0.49) and ICC (0.01 to 0.15).

As specified in the protocol, analyses of data from the internal pilot provides empirical point estimates for these parameters for use in the updated power analyses presented here. At the time of writing (August 2024), a total of 43 families (21 allocated to MBT and 22 to TAU) with 61 CYP (30 MBT, 31 TAU) had complete baseline/T1 and outcome (T2, post intervention) mothers SDQ. Analyses of these 61 CYP in 43 families has been used to provide empirical estimates for ICC and explanatory power at the family and CYP levels.

The power analyses were undertaken using equation 1.0 below and checked using the PowerUp! software (Dong & Maynard, 2013, sheet CRA2_2r).

$$[1.0] \quad MDES_{2LCRT} \sim M_{J-m-2} \sqrt{\frac{1}{P(1-P)}} \sqrt{\frac{ICC(1-R_{Fam}^2)}{J} + \frac{(1-ICC)(1-R_{CYP}^2)}{nJ}}$$

For a 2-level CRT design, the MDES is influenced by (estimates updated from analyses of pilot data):

- n=number of CYP per family = **1.4** (updated from 2.0 in protocol).
- J = number of families (**90** at pilot, allowed to vary up to **400** see below).
- P = proportion of families allocated to intervention group (= **0.50**).
- m= number of (level 2) covariates used (which will include: group membership, family-level pre-test, 4 (dummy) variables used for minimisation ~ **6** variables).
- M_{J-m-2} is the group effect multiplier value of the t-distribution for a 2-tailed test with alpha=0.05 & beta=0.80.
- ICC is the family level ICC = **0.27** (updated from 0.01 to 0.15 in protocol). This is the proportion of variance of the outcome at level 2 (between-family variance).

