The updated power analyses presented here illustrate that, even with fewer CYP per family than initially estimated, a smaller sample of families is likely to be sufficient sensitivity to detect an MDES of 0.20 sds or higher than was estimated at protocol. With 250 families (and 350 CYP), the MDES estimate is 0.17 sds. With an attrition rate of 10%, assuming attrition was random, the indicative MDES estimate is 0.18 sds. With an attrition rate of 20%, assuming attrition was random, the indicative MDES estimate is 0.19 sds.

Therefore, following the updated power analysis, the recommended sample size for the evaluation of the Tavistock MBT-PP programme is reduced from 350 families (700 CYP) to be 250 families (350 CYP).

Analysis

Research questions were operationalised as follows:

RQ1 Does MBT-PP (compared to TAU) delivered to parents experiencing IPC lead to lower externalising and internalising behaviours in children aged 8-14 (as measured by the SDQ total 'difficulties' scale)?

This splits into two separate RQs (SDQ total difficulties for mothers and for fathers).

RQ1a Does MBT-PP (compared to TAU) delivered to parents experiencing IPC lead to lower externalising and internalising behaviours in children aged 8-14 as measured by the mother's SDQ total 'difficulties' scale? – PRIMARY OUTCOME RQ1

RQ1b Does MBT-PP (compared to TAU) delivered to parents experiencing IPC lead to lower externalising and internalising behaviours in children aged 8-14 as measured by the father's SDQ total 'difficulties' scale? – SECONDARY OUTCOME RQ1

RQs 2-8 inclusive also all examine secondary outcomes, and, apart from those where the outcome variable comes from CYP rather than parents (RQ2 regarding child wellbeing and RQ4 regarding child perception of IPC), they split into a) maternal report and b) paternal report, as per RQ1.

RQ2 Does MBT-PP (compared to TAU) delivered to parents experiencing IPC lead to higher wellbeing in children aged 8-14 (as measured by the Stirling Children's Well-being Scale)?

RQ3 Does MBT-PP (compared to TAU) delivered to parents experiencing IPC lead to lower IPC reported by parents (as measured by the O-Leary-Porter Scale)?

RQ3a Does MBT-PP (compared to TAU) delivered to parents experiencing IPC lead to lower IPC reported by mothers (as measured by the O-Leary-Porter Scale)?

RQ3b Does MBT-PP (compared to TAU) delivered to parents experiencing IPC lead to lower IPC reported by fathers (as measured by the O-Leary-Porter Scale)?

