The analysis described in this plan follows YEF analysis guidance¹. An Intention to Treat (ITT) approach will be taken whereby CYP are identified as members of the intervention or control group solely based on their random allocation and regardless of whether their parent(s) participate in the intervention or not. The ITT approach best preserves random allocation. This means that the only difference between the two group (of families/parents) is that one group received the Tavistock MBT-PP programme and the other groups (TAU) did not. All other differences between these groups are (fixed to be) random at baseline and, assuming zero attrition, this assumption is maintained at outcome. It is the ITT analysis of the primary outcome (mothers reported SDQ total difficulties score) that this clustered RCT is statistically powered to detect. Specifically and assuming zero attrition, if a difference between the intervention and control group is observed to be 0.17 sds or higher, this would represent evidence that participation in the Tavistock programme caused this positive (or negative) impact within pre-specified levels of statistical significance ($p < 0.05$, two-tailed) and statistical power (0.80 or higher). As detailed below, following the ITT analysis of the primary outcome, missing data and Compliers Average Causal Effect (CACE) analyses will be undertaken.

An ITT approach will also be used for analyses of secondary outcomes. Follow-on analyses of the primary outcome will estimate the Compliers Average Causal Effect (CACE); the impact of the programme for CYP located in families/parents known to have engaged in the MBT-PP programme as was intended (see below).

All analyses will be undertaken using STATA v18. Specifically, parameter estimates will be obtained using the 'mixed' suite of commands in the STATA software. For primary and secondary outcomes, pre-test covariates will be included at both CYP and cluster (family) levels. These will be centred as recommended by Hedges & Hedberg (2007 & 2013) and Konstantopoulos (2008). Specifically, at the CYP level, scores will be centred around the cluster (family/parent) mean and at the family/parent level the cluster(family) means will be centred around the overall cluster-level grand mean. Other than the constant term, centring

¹ <https://youthendowmentfund.org.uk/resources-for-evaluators/>

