These latter models will be tested in the same way as outlined above for the models with child internalising and externalising behaviours as the final latent variable in the causal chain.

Imbalance at baseline

The characteristics of the MBT and TAU group families and CYP as measured prior to randomisation will be compared. At the CYP level, this will include the T1 mothers SDQ-TD primary outcome and X secondary outcomes, ethnicity, age, gender, EAL and SEND status. At the family level this will include the three minimisation variables (relationship status, CYP ages and parental ethnicity) along with family size and the aggregated primary and secondary outcomes. For scale/continuous variables, means and standard deviations for the MBT and TAU groups will be reported and the difference converted into a Hedges g effect size by dividing the mean difference (MBT – TAU) by the pooled standard deviation. For categorical variables, counts and percentages will be reported.

The analyses of balance at baseline will be replicated for the subsample of CYP included in the final impact analysis for the primary outcome; a complete case subsample. In the case of very low attrition, baseline and complete case analyses should reflect each other. However, as attrition increases, differences are likely to be seen. These analyses will inform the missing data analyses described in the next section.

Missing data

The amount of missing outcome data for the mothers SDQ-TD primary outcome will be summarised, and reasons for missing data discussed in the report, where available. If greater than 5% of CYP have missing mothers SDQ-TD, multi-level logistic regression will be used to model presence or absence of the primary outcome including all available CYP and family-level baseline data as fixed effects, and family as a random effect. Significant variables and possible reasons for the missing data will be discussed in the report.

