A binary variable that distinguishes CYPs with a missing T2 mothers SDQ-TD (= 1) from CYPs with a T2 score (= 0) will be created. Bivariate patterns of missingness will be described (e.g. % missing across all variables included in the ITT analyses plus auxiliary variables at the CYP and family levels) and then modelled using a multilevel logistic regression model with the CYP-level binary missing variable as outcome and the same variables used to examine baseline balance included as explanatory variables at CYP- and family-levels. This represents the ‘drop-out’ model which will provide estimates of the association between the included variables and the probability of being missing from the final impact analysis for the primary outcome.

If none of the covariates included in the ‘drop-out’ model are observed to account for a statistically significant amount of variation in the missing data outcome, imputation will not be feasible. This would lead us to cautiously conclude that the data are missing at random and would discuss the implications of this (which will depend upon the quantity of missing data) in the evaluation report.

If we observe that covariates account for a statistically significant amount of variation in the missing data outcome, we will conduct multiple imputation (MI) analysis to impute the

missing data. The MI analysis will be undertaken using the STATA ‘MI Impute’ command used to impute missing values on the primary outcome (StataCorp, 2023). A ‘burn-in’ of 20 will be used (meaning that the first 20 iterations will be discarded to allow the iterations to converge to the stationary distribution before the imputation) and 100 imputed datasets will be created. The impact analysis for the primary outcome will then be rerun within the imputed datasets using the STATA ‘MI Estimate’ command with Rubin’s rules (Rubin, 1987) used to combine the multiply imputed estimates of the β_1 coefficient in equation 2.0. The coefficient estimates for the original complete case and MI analyses will be compared and discussed in the evaluation report.

Compliance

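### The drop-out model, and so the decision to impute, leaves out allocated arm and MBT-PP attendance, and the imputation predictors are not stated; adding both is a cheap improvement

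*SAP*

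**What the plan says.** The SAP's Analysis section sets an ITT question: children are analysed as allocated, "regardless of whether their parent(s) participate in the intervention or not". The protocol's Analysis section makes the primary set those children "with complete baseline/outcome data regardless of whether their family is classed as being 'compliant", that is, complete cases. It treats the imputed re-analysis as a sensitivity analysis.

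The SAP's Missing data section describes the model for missing T2 scores twice. The first description is of a multilevel logistic regression "including all available CYP and family-level baseline data as fixed effects". The second uses "the same variables used to examine baseline balance included as explanatory variables at CYP- and family-levels". The balance list, under Imbalance at baseline, holds baseline scores, child characteristics, the minimisation variables and family size. Allocated arm and attendance are not in it. Auxiliary variables are mentioned, unnamed, but for the bivariate description of missingness and not for the model.

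If no variable in the drop-out model is significant, the SAP cautiously concludes that data are missing at random and does not impute. If one is, multiple imputation follows. For that step the SAP gives the Stata command, the burn-in and the number of datasets, but no predictors.

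Attendance is available. The protocol's MBT-PP administrative data section lists "how many therapy sessions were attended per family" among the data obtained from the provider. The SAP's Compliance section turns it into a six-session indicator for the complier analysis and gives it no role for missing T2.

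**The concern.** Leaving therapy early is one plausible route to a missing T2 questionnaire. The SAP's Design overview places T2 after therapy: "Once treatment has completed, families complete post-intervention assessments". If families who leave are less likely to respond, the MBT-PP families with a T2 score contain more attenders than the arm as randomised. If leavers also gain less, the observed MBT-PP mean is too favourable for an ITT estimate. Imputing from baseline and arm gives absent leavers the mean of that attender-rich group, so the bias is carried over.

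There are two consequences. First, where loss depends on attendance and little else, a baseline-only drop-out model may find nothing significant, and the plan would then not impute. Second, where imputation is run, the SAP compares it with the complete-case result. Two estimates sharing one bias would agree, and the agreement could be read as evidence that missing data did no harm.

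**Working it through.** **The plan's own figure, for scale.** SAP equation 1.0 with J = 250, n = 1.4, ICC = 0.27, family R² = 0.61, CYP R² = 0.75, m = 6, P = 0.5:

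- Standard error: 2 × √(0.27 × 0.39/250 + 0.73 × 0.25/350) = 0.0614 SD.
- Multiplier: t(0.975, 242) + t(0.80, 242) = 2.813.
- MDES: 2.813 × 0.0614 = 0.173.

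This matches the SAP: "With 250 families (and 350 CYP), the MDES estimate is 0.17 sds". The Missing data section states no figure of its own.

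**Inputs.**

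- Compliance p = 0.75 or 0.50, from the edges of the bands in protocol Appendix A, criterion 3. These are thresholds, not observed rates.
- MBT-PP arm loss L = 10% or 20%, the SAP's two attrition scenarios.
- True ITT effect = -0.20 SD, the target effect in the SAP's sample size section. Negative means fewer difficulties.
- No effect below six sessions. This is an assumption; the instrumental-variable complier analysis needs it too.
- Families below six sessions are RR = 3 or 5 times as likely to lack T2. This is an assumption; the documents give nothing.
- TAU loss has the same L and is unrelated to would-be attendance. This is an assumption, relaxed below.

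**Formulas.** Loss among attenders is r_c = L/(p + RR(1-p)); among the rest it is r_n = RR × r_c. The attender share among observed MBT-PP families is p′ = p(1-r_c)/(1-L).

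- Complete case, or imputation from baseline plus arm: true effect × p′/p.
- Imputation from baseline without arm: missing scores in both arms are drawn from one pool, so the observed difference is multiplied by (1-L). The result is true effect × (1-r_c).

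Worked case, p = 0.75, L = 0.20, RR = 3: r_c = 0.20/1.5 = 0.133; p′ = 0.75 × 0.867/0.80 = 0.8125; ratio = 0.8125/0.75 = 1.083; estimate = -0.217. Without arm: -0.20 × 0.867 = -0.173.

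| L | p | RR | ratio | complete case, or imputation with arm | imputation without arm |
|---|---|---|---|---|---|
| 10% | 0.75 | 3 | 1.037 | -0.207 | -0.187 |
| 10% | 0.75 | 5 | 1.056 | -0.211 | -0.190 |
| 10% | 0.50 | 3 | 1.056 | -0.211 | -0.190 |
| 10% | 0.50 | 5 | 1.074 | -0.215 | -0.193 |
| 20% | 0.75 | 3 | 1.083 | -0.217 | -0.173 |
| 20% | 0.75 | 5 | 1.125 | -0.225 | -0.180 |
| 20% | 0.50 | 3 | 1.125 | -0.225 | -0.180 |
| 20% | 0.50 | 5 | 1.167 | -0.233 | -0.187 |

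At 30% loss, the top of the amber band for Parent 1 attrition (Appendix A, criterion 9), the ratios run from 1.14 to 1.29.

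**Simulation.** Large single-level simulations, with baseline R² of 0.65, reproduce these values. At p = 0.75, L = 0.20, RR = 3 they give -0.217 for complete case, -0.217 for imputation with arm, -0.173 without arm, and -0.200 once attendance is added.

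**When the direction changes.** These runs set the true effect at -0.17.

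- Loss unrelated to attendance: no bias.
- Leavers with the same effect as attenders: -0.168.
- Leavers who gained more: -0.153.
- Leavers with a 0.3 SD better prognosis: -0.164.
- Attenders lost more often (30% against 10%, p = 0.75; mixture formula): -0.159.

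**Limit of the remedy.** Suppose the same kind of family is also lost in TAU, where attendance is not observed, and its prognosis is worse by δ. Adding attendance then corrects only the MBT-PP arm, and the estimate falls short by δ(p′-p). At 20% loss and δ = 0.3 SD it lies between -0.172 and -0.181; at δ = 0.1 SD, between -0.191 and -0.194. Without attendance the overstatement is (0.20/p)(p′-p). Adding attendance therefore gives the smaller error when δ is below 0.20/p, which is 0.27 SD at 75% compliance and 0.40 SD at 50%. In this scenario the two versions lie on either side of the truth.

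**The case against.** A reader might infer that the plan does overstate benefit. The documents do not support that, for several reasons.

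- **The imputation model is unstated.** The baseline list belongs to the drop-out model. Carrying it over to the imputation is an inference, and a literal carry-over would omit arm too and shrink the effect. This stands; overstatement requires a model with arm and without attendance, or the complete-case estimate itself.
- **The link between leaving and missing T2 is not documented.** The SAP's Primary outcome analysis fixes T2 at 16 weeks after minimisation, not at the end of therapy. Vouchers reward questionnaires in both arms, with a bonus for all three time points, and Gateway Leads support collection. This stands, and it is why the size is conditional.
- **The compliance bands count clients, while SAP compliance counts families with at least one parent at six sessions.** The family rate can be higher, which lowers the bias. This stands.
- **The size is modest.** At 10% loss the shift is 0.007 to 0.015 SD, against a standard error of about 0.061 SD. At 20% loss it is 0.017 to 0.033 SD. This stands.
- **Only a sensitivity analysis would change, and other checks exist.** Balance is repeated in the complete-case sample, reasons for loss are reported, and the protocol compares compliant with non-compliant participants. This stands in part: none of these checks brings attendance into an estimate of the effect, and imputation is the only planned re-estimate for missing T2.

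**Conclusion.** The point holds as a cheap improvement in specification, not as a demonstrated bias. The drop-out model, and hence the decision to impute, rests on baseline variables only. The predictors of the imputation are not given, and neither arm nor attendance is named for either step.

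If families below six sessions are three to five times as likely to lack T2 and gain nothing, with 50-75% compliance, the complete-case estimate and an imputation from baseline plus arm both overstate the ITT effect by about 4-7% at 10% loss and 8-17% at 20% loss. Imputation does not create this bias; it repeats it, so agreement between the two is weak evidence. If arm is omitted as well, the imputed effect shrinks to about -0.17 to -0.19 against a true -0.20, and the complete-case and imputed results differ because of the model rather than the data. With loss unrelated to attendance there is no bias from this source, and other assumptions reverse it.

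**What to change.** In the SAP's Missing data section:

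1. Add allocated arm and MBT-PP attendance (sessions attended or the six-session indicator, coded 0 in TAU so that it acts as a term within the MBT-PP arm) to the drop-out model.
2. State the imputation predictors: arm, attendance, the baseline variables, and the mother's T3 SDQ total difficulties score where available.
3. Keep equation 2.0, without attendance, as the analysis model, so the estimate remains ITT.
4. Report T2 completion by attendance group in the MBT-PP arm, so that readers can see whether the issue arises.
5. Present the imputation with attendance as a sensitivity analysis alongside one with arm and baseline but without attendance.

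No new data or participants are needed. The standard error rises slightly, by about 0-4% in simulation (for example 0.085 to 0.086 at 20% loss), because few families below six sessions will have a T2 score: about 19 of 31 at 75% compliance, 20% loss and a three-fold link (125 × 0.25 = 31; 31 × 0.60 = 19). The method can also over-correct if similar families are lost in TAU, which is the reason for showing both versions.
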